10.3.2. Criteria for Adjustment or Stopping Dose of Pembrolizumab

Refer to Table 18 for dose modification and management guidelines for IRAEs related to pembrolizumab. Additional guidelines from the NCCN on the diagnosis and management of IRAEs can be found in Appendix E. Rechallenge with pembrolizumab is not permitted for the following:

- Any IRAE that requires permanent discontinuation of study drug according to the guidelines in Table 18.
- Any severe (Grade 3) or life-threatening (Grade 4) infusion-related reaction.

If it is determined that pembrolizumab must be permanently discontinued based on the above criteria, dosing with XmAb18087 must also be discontinued.

10.4. Study Treatment Packaging and Labelling

10.4.1. Packaging and Labelling of XmAb18087

XmAb18087 and the IV Solution Stabilizer will be supplied in single-use glass vials.

XmAb18087 and the IV Solution Stabilizer will be supplied by Almac. IMPs will be packaged and labeled according to applicable local and regulatory requirements.

10.4.2. Storage of XmAb18087

Vials containing XmAb18087 and IV Solution Stabilizer must be stored under refrigeration at in an appropriately secured area accessible only to the pharmacist, the PI, or a duly designated person. Since XmAb18087 does not contain preservatives, opened vials of XmAb18087 must be used within 24 hours.

10.4.3. Preparation of XmAb18087

Note that XmAb18087 has PD effects in vivo at very low concentrations and therefore each product vial must be highly diluted before administration.

Prior to administration, XmAb18087 will be diluted to the required final concentration in 1 or more ethylene/polypropylene copolymer infusion bags

. Prior to dilution, the vial containing parenteral drug product should be inspected visually. If particulate matter and/or discoloration are noted, drug should not be administered, and the Sponsor should be notified. After dilution, the bag containing XmAb18087 should be gently inverted 2 to 3 times to mix the solution. **THE BAG MUST NOT BE SHAKEN**; excess agitation may cause aggregate formation. See the XmAb18087 Pharmacy Manual for additional details.

10.4.4. Packaging and Labeling of Pembrolizumab

Pembrolizumab will be obtained from commercial sources and administered to subjects in the combination therapy cohorts on Day 15 of each 42-day cycle as directed by the package insert (Keytruda® Package Insert, 2020).

Version 1.0 Page 76 of 145

Xencor, Inc

10.4.5. Storage of Pembrolizumab

Store under refrigeration at 2 °C to 8 °C, do not freeze, do not shake, and protect from light, as per the pembrolizumab prescribing information (Keytruda® Package Insert, 2020).

10.5. Study Treatment Accountability, Handling, and Disposal

Detailed instructions and procedures for study-drug dispensing are included in the Pharmacy Manual.

Accurate accounting of all study drug must be maintained. The PI agrees to keep an inventory of study drugs using local investigational pharmacy drug accountability logs. Drug disposition records must be kept in compliance with applicable guidelines and regulations.

These records shall include dates, quantities, batch numbers, expiry dates, and the unique code numbers assigned to the study drug and to the study subjects.

The Investigator shall be responsible for ensuring records adequately document that the subjects were provided the doses specified in the protocol and that all study drug received from the Sponsor is reconciled.

Upon completion or termination of the study, any used or partially used vials, unused study medication, diluted drug dosing solutions, or IV Solution Stabilizer should be destroyed in compliance with local investigational pharmacy policies or returned to the Sponsor or its designee.

Version 1.0 Page 77 of 145

11. ASSESSMENT OF SAFETY

Adverse event reporting will begin with the signing of the informed consent document (Screening) and will continue until the end of the subject's participation in the study: ie, until a subject has discontinued or completed the study.

Safety and tolerability assessments will include the following:

- AEs
- Vital signs
- PE findings
- Clinical laboratory safety assessments
- ECG parameters

Biomarkers of CRS (IL-2, IL-6, IL-8, IL-10, IFN- γ , IL-13, IL-1B, and TNF- α) will also be collected as additional safety information.

Details for management of hypersensitivity reactions, CRS, and neurologic toxicities are provided in Section 11.3.2, 11.3.3.3, and 11.3.3.4, respectively, as well as in Section 11.3.3 and Appendix C of this protocol.

11.1. Adverse Events

11.1.1. Definitions

11.1.1.1. Adverse Event

An AE is any untoward medical occurrence in a study-subject administered IMP. The AE does not necessarily have a causal relationship with this treatment. An AE can therefore be any unfavorable and unintended sign (including a clinically significant abnormal laboratory finding), symptom, or disease temporally associated with the use of an IMP, whether or not considered related to the IMP. Adverse events may include the onset of new illness and the exacerbation of preexisting conditions.

Other untoward events occurring in the framework of a clinical study will be recorded as AEs, eg, those occurring during treatment-free periods (including Screening or post-treatment follow-up periods), in association with study-related procedures and assessments, or under placebo. For IMPs, lack of efficacy may be an expected potential outcome and should not be reported as an AE, unless the event is unusual in some way, eg, greater in severity.

Concomitant illnesses, which existed prior to entry into the clinical study, will not be considered AEs unless they worsen during the treatment period. Preexisting conditions will be recorded as part of the subject's medical history.

11.1.1.1.2. Serious Adverse Event

AEs are classified as "serious" and "non-serious" for regulatory reporting purposes. The classification determines the procedures used to document and report the AE.

Version 1.0 Page 78 of 145

An SAE is an AE occurring during any study phase (ie, baseline, treatment, washout, or follow-up), and at any dose of the investigational product or comparator, that fulfills one or more of the following:

- Results in death
- Is life-threatening; this means that the subject was at immediate risk of death at the time of the event. It does not mean that the event hypothetically might have caused death if it were more severe.
- Requires inpatient hospitalization or prolongation in existing hospitalization
- Results in persistent or significant incapacity or substantial disruption of the ability to conduct normal life functions
- Is a congenital anomaly or birth defect
- Is an important medical event. Important medical events are events that may not be immediately life threatening but are clearly of major clinical significance. They may jeopardize the patient and may require intervention to prevent one of the other serious outcomes listed above.

Examples of such medical events include allergic bronchospasm requiring intensive treatment in an emergency room or in a physician's office, blood dyscrasias or seizures that do not result in subject hospitalization, and the development of drug dependency or drug abuse. Hospitalizations for planned surgical/medical elective procedures will not be reported as SAEs. In addition, hospitalizations of \leq 24 hours will not be reported as SAEs. A death due to disease progress will not be considered an expedited report.

The following will **not** be reported as an SAE:

- Hospitalization for planned surgical/medical elective procedures per protocol for study drug administration, any admission required for disease assessments, or any admissions planned prior to enrollment (eg, planned surgical/medical elective procedures) will not be recorded/reported as an SAE.
- Hospitalization or death due to disease progression. Signs/symptoms and conditions related to disease progression of the primary condition under the investigation (eg, tumor-related pain, metastasis, new lesions, etc).

A distinction should be drawn between serious and severe AEs. Severity is a measure of intensity whereas seriousness is defined by the criteria above. For example, a mild degree of gastrointestinal bleeding requiring hospitalization for monitoring purposes would be considered an SAE but is not necessarily severe. Similarly, an AE that is severe in intensity is not necessarily an SAE. For example, alopecia may be assessed as severe in intensity but would not be considered an SAE.

Medical and scientific judgment should be exercised in deciding if an AE is serious and if expedited reporting is appropriate.

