11.1.4.1. Deaths

Should a death occur within the study period or within 28 days after the last administration of study drug (or until the subject initiates other anticancer therapy, whichever comes first), an AE form and an SAE form should be completed, detailing the AE that resulted in the death (death is an outcome, not an event). The SAE must be reported to the Medical Monitor within 24 hours. The report should contain a comment regarding the coinvolvement of progression of disease, if appropriate, and should assign main and contributory causes of death.

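### The protocol gives contradictory SAE rules for deaths due to disease progression within its death-reporting window

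*Protocol*

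**What the plan says.** Protocol Section 11.1.1.1.2 defines an SAE as an AE meeting at least one listed criterion. Two of the criteria are "Results in death" and "Requires inpatient hospitalization or prolongation in existing hospitalization". The section then makes three statements that narrow this:

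- Hospital stays of up to "24 hours will not be reported as SAEs".
- "A death due to disease progress will not be considered an expedited report".
- In a closing list of items not reported as SAEs: "Hospitalization or death due to disease progression".

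Protocol Section 11.1.4.1 (Deaths) opens with "Should a death occur within the study period or within 28 days after the last administration of study drug", and its window closes earlier if the subject starts other anticancer therapy. For such a death, "an AE form and an SAE form should be completed, detailing the AE that resulted in the death". The section calls the event an SAE, sets a 24-hour deadline for telling the Medical Monitor, and asks the report to address any part that progression played and to assign main and contributory causes.

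TESAEs are named in the Synopsis (Criteria for Evaluation) and in Protocol Section 14.6, which has them summarised by MedDRA class and term. SAP Section 5.1 reports early termination with 4 subjects enrolled (2 in Part A, 2 in Part C) and reduces the output to listings. SAP Section 11.2 lists all deaths on study, including those reported on the End of Study and long-term follow-up forms.

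**The concern.** A death from progression inside the Section 11.1.4.1 window is excluded from SAE reporting by one section and sent to an SAE form within 24 hours by another. Two sites applying the protocol in good faith could classify the same death differently.

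The trial is open-label (Protocol Section 9.4). Under Section 11.1.1.1.2, the investigator's attribution of a death to progression would by itself keep that death out of 24-hour SAE reporting and out of the TESAE summary. Under Section 11.1.4.1 the death would be reported and the attribution recorded as a comment that others can review. With a new T-cell-engaging antibody in advanced cancer, telling a progression death from a treatment-related one can be hard, so the difference is of practical importance.

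**Working it through.** The protocol states no figure that depends on this point. The check is a comparison of the two sections, followed by a simple scale.

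**1. Which deaths are affected**

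| Death | Section 11.1.1.1.2 | Section 11.1.4.1 | Agree? |
|---|---|---|---|
| In window, caused by a separate AE | SAE | SAE form, 24 hours | Yes |
| In window, AE and progression both contributing | SAE, unless the investigator attributes the death to progression | SAE form, 24 hours, comment on progression | Depends on attribution |
| In window, due to progression | Not an SAE | SAE form, 24 hours, comment on progression | No |
| Outside the window | Not an SAE if due to progression | Does not apply | No conflict |

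The conflict lies in the third row, and in the second row when the death is attributed to progression.

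**2. Section 11.1.1.1.2 read on its own.** It says that progression deaths are not expedited reports and, in its closing list, that they are not SAEs. The second statement is the stronger. If it governed, the first would be redundant, because a death that is never reported as an SAE needs no waiver from expedited reporting.

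**3. What depends on it.** Section 14.6 defines treatment emergence but gives TESAE no separate definition, so a TESAE is an SAE that is treatment-emergent. Take a subject whose only candidate TESAE is a progression death in the window, with onset or worsening after treatment began. That subject counts 0 under Section 11.1.1.1.2 and 1 under Section 11.1.4.1.

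**4. Scale of one such subject**

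- Enrolled subjects (SAP Section 5.1), assuming all 4 were dosed: 1/4 = 25 percentage points on the subject-level TESAE rate.
- Planned maximum (Protocol Section 7.5): 1/142 = 0.7 percentage points.

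The documents do not give the number of such deaths. Among the enrolled subjects it can only be between 0 and 4.

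**5. Short admissions.** The hospitalization criterion has no minimum stay. The exemption for stays of 24 hours or less is a stated exception in the same section. It does not say what happens when the event behind a short stay also meets another criterion, such as life-threatening or important medical event. The criteria list makes that event serious, while the exemption, read literally, removes the admission from reporting.

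**The case against.** The best defence of the death rules is that they can be harmonised. Section 11.1.4.1 asks for the AE that led to death and for the contribution of progression, and the protocol's AE definition says that lack of efficacy is ordinarily not an AE. On that reading, Section 11.1.4.1 covers deaths with a separate causal AE, and Section 11.1.1.1.2 covers deaths from progression alone. The reading is possible and would shrink the gap. But Section 11.1.4.1 contains no such limit: it is triggered by a death within a time window. The sentence on expedited reports also points the other way, although it does not prove which rule was intended.

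The defence is right about consequences. The SAP produces no TESAE rate and lists every death whatever its SAE status, so no death should disappear from the report. TESAEs are not named among the primary endpoints in Protocol Section 14.3.1 or the endpoints in SAP Section 3.3.

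It is also largely right about short admissions. A reader might infer that the 24-hour exemption contradicts the SAE definition, since the protocol says "a mild degree of gastrointestinal bleeding requiring hospitalization for monitoring purposes would be considered an SAE". The documents do not support this. The exemption is explicit, and the example separates seriousness from severity without giving a length of stay. Short cytokine release syndrome (CRS) admissions would not be lost from the CRS analysis either: incidence and severity of CRS is a primary endpoint in its own right, and the objective that counts CRS-related SAEs is exploratory (Protocol Section 6.3). Only the missing proviso remains.

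**Conclusion.** The contradiction between Sections 11.1.1.1.2 and 11.1.4.1 is real, and the text does not resolve it. It leaves SAE reporting and the protocol's TESAE summary ambiguous for deaths due to progression in the study period or within 28 days of the last dose, up to the start of other anticancer therapy.

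A reader might go further and infer that TESAE counts as a whole are undefined. They are not: the SAE criteria and treatment emergence are both defined, and the ambiguity is confined to these deaths and to short admissions that also meet another criterion. Nor can the planned 142 subjects be used to project a number of affected deaths. Only 4 were enrolled, and the documents give no rate of progression deaths in the window.

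The practical size is 0 to 4 subjects. Each affected subject would be worth 25 percentage points of a TESAE rate that the SAP does not plan to compute, assuming all 4 were dosed and the subject had no other TESAE. The finding therefore bears on SAE classification and reporting, not on any SAP table.

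**What to change.** 1. Replace the two death rules with one, stated in both sections. The protocol's own sentence on expedited reports offers a consistent version: every death in the window goes on an SAE form with a comment on progression, and only expedited reporting is waived for progression deaths. The text should then say what expedited means, and in particular whether the 24-hour notice to the Medical Monitor still applies. The documents do not show which rule the sponsor intended, so the sponsor must confirm it.
2. In the clinical study report, state which rule was applied to the 4 enrolled subjects. Check the death listing (SAP Section 11.2) against the SAE listing, and explain any death that appears in only one.
3. Secondarily, add to the exemption for admissions of 24 hours or less that an event meeting any other seriousness criterion is still reported as an SAE.

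The cost is a few sentences of protocol wording, possibly a few additional SAE forms, and a listing check on 4 subjects. No analysis or sample size changes.

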11.1.1.3. Abnormal Laboratory Values

Clinically significant abnormal laboratory results which are not caused by the underlying disease or are not consistent with the subject's medications will be recorded as AEs and the relationship

Version 1.0 Page 79 of 145

Protocol XmAb18087-02

Xencor, Inc

to the study drug will be indicated as below. Laboratory values outside the normal range will be assigned one of the following categories by the Investigator or designee:

- 1. Not clinically significant, minor out of range value or finding. AE No
- 2. Not clinically significant, out of range value or finding explainable by anticipated or known effect of study drug or concomitant drugs. AE No
- 3. Clinically significant but consistent with the subject's underlying disease. AE No
- 4. Clinically significant out of range value or finding. AE Yes

In general, a clinically significant laboratory value or finding would require some diagnostic or therapeutic intervention other than repeating the test.

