11.3.3. Treatment Guidelines for Cytokine Release Syndrome

11.3.3.1. Use of Tocilizumab for Cytokine Release Syndrome

Tocilizumab is a therapeutic antibody that interferes with binding of IL-6 to the IL-6 receptor. It has been used to decrease the severity and possibly mortality of severe CRS (Frey, 2017), and early administration may be useful in improving outcomes. Below are suggested guidelines for its use:

Version 1.0 Page 88 of 145

- Sufficient tocilizumab (dose of 8 mg/kg) should be readily available to the area where subjects are receiving their infusions and being observed post infusion.
- Prompt tocilizumab therapy should be strongly considered if:
 - Oxygen saturation falls below 90% on room air, **OR**
 - Systolic blood pressure falls 20 mm Hg below predose measurements and below 100 mm Hg, **OR**
 - Temperature of > 38 °C (100.4 °F) in the presence of new or worsening dyspnea and/or tachypnea and/or rigors and/or tachycardia (heart rate [HR] > 110 bpm), OR
 - Early discovery of hepatic transaminase elevation. (Note that peak transaminase elevation appears to occur within 24 hours, so that it is unlikely that tocilizumab treatment on the day after study drug administration would affect the course or outcome in the absence of concurrent symptoms or signs of CRS).
- Repeat dosing of tocilizumab may be necessary if signs and symptoms persist or return after initial treatment.

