14.3. Study Endpoints

14.3.1. Primary Endpoints

The primary endpoints are as follows:

- Safety of (1) XmAb18087 monotherapy in MCC and SCLC, and (2) XmAb18087 and pembrolizumab combination therapy in MCC, as assessed by the following:
 - Incidence of treatment-emergent AEs (TEAEs)
 - Incidence of clinically significant changes in safety laboratory tests, PE findings, vital signs, and ECGs

Version 1.0 Page 99 of 145

- Incidence and severity of CRS
- Efficacy of (1) XmAb18087 monotherapy in MCC and SCLC, and (2) XmAb18087 and pembrolizumab combination therapy in MCC using RECIST 1.1 assessment of CT/MRI imaging, as well as aggregate data, for the following:
 - ORR
 - CR rate
 - PR rate

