### **11.3. Clinical Laboratory Evaluations**

Hematology, chemistry, coagulation, viral serology, and urinalysis laboratory values at each scheduled time point will be listed. Laboratory results outside predefined normal ranges and reported as clinically significant by investigators will be flagged in the data listings.

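### Protocol 11.1.1.3 lets attribution to study drug count against recording a laboratory AE, and SAP 11.3 omits the grades and high/low flags that would make such values visible

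*Protocol*

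**What the plan says.** Protocol 11.1.1.3 opens by stating which clinically significant abnormal results become AEs: those "which are not caused by the underlying disease or are not consistent with the subject's medications will be recorded as AEs", with their relationship to study drug then noted. Four classes follow:

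- Class 1 covers minor values that are not clinically significant, and sets no AE.
- Class 2 is "Not clinically significant, out of range value or finding explainable by anticipated or known effect of study drug or concomitant drugs. AE No".
- Class 3 is "Clinically significant but consistent with the subject's underlying disease. AE No".
- Class 4 is "Clinically significant out of range value or finding. AE Yes".

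The section ends with a working test of significance: in general, whether the value calls for work-up or treatment beyond a repeat test.

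Protocol 11.1.1.1 counts clinically significant laboratory findings among AEs when they are "temporally associated with the use of an IMP, whether or not considered related to the IMP". Two of the primary safety endpoints in Protocol 14.3.1 depend on these rules: the incidence of TEAEs, and "Incidence of clinically significant changes in safety laboratory tests, PE findings, vital signs, and ECGs".

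For reporting, Protocol 14.6 grades laboratory tests by CTCAE v5.0 and marks every value outside normal limits as high or low in the subject listings. SAP 11.3 lists all scheduled values but gives a narrower flag rule: "Laboratory results outside predefined normal ranges and reported as clinically significant by investigators will be flagged in the data listings". It does not mention laboratory grades. SAP 5.1, which records changes from the protocol, says that 4 subjects were enrolled (2 in Part A, 2 in Part C) and that only listings will be produced. It does not mention the laboratory flags or grades.

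**The concern.** In safety reporting, the cause of an event is normally an attribute of a recorded event. It is not a condition for recording it. Protocol 11.1.2.2 follows that principle with a separate five-level causality scale. Section 11.1.1.3 mixes the two: a known effect of the investigational drug is part of the description of a class that is not recorded, and fit with the subject's medications appears in the sentence that says what is recorded.

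The laboratory changes most exposed to this are those that XmAb18087 is expected to cause, and more values could qualify as the drug's effects become better known. A value in class 2 is not a TEAE and does not count as a clinically significant change. It may also drop out of the AESC count, because Protocol 7.8 defines an AESC as an AE or a clinically significant laboratory value, and its causal exemption covers malignancy and concurrent disease, not study drug.

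Grades and flags that do not depend on the investigator's opinion would show the reader such values anyway. SAP 11.3 does not provide them.

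**Working it through.** The plan states no figure on this point and no arithmetic applies. The check follows each kind of value through the rules.

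**Step 1. The four classes taken alone.**

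| Value | Class | AE, and TEAE if emergent | Laboratory endpoint (14.3.1) | SAP 11.3 flag | Listed |
|---|---|---|---|---|---|
| Explained by study drug, not clinically significant | 2 | No | No | No | Yes |
| Explained by study drug, clinically significant | 4 | Yes | Yes | Yes | Yes |
| Fits underlying disease, clinically significant | 3 | No | Yes, on its wording | Yes | Yes |

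Of the two rows explained by study drug, one is left out and one is kept. The outcome depends on the significance call.

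**Step 2. How firmly the significance call is fixed.** Class 1 is limited to minor values. Class 2 has neither that limit nor a CTCAE ceiling, and the intervention test is qualified as a general guide. A high-grade value that needs no intervention can therefore be placed in class 2.

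A transient Grade 3 ALT rise shows the room for judgement:

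- Protocol 11.3.2 lists transaminitis among the complications of CRS, so the rise is an anticipated effect.
- Protocol 11.3.3.1 names early transaminase elevation as a reason to consider treatment, but also notes that "peak transaminase elevation appears to occur within 24 hours" and that next-day treatment is unlikely to change the course without other signs of CRS.
- CRS grading (11.3.1) rests on fever, hypotension and hypoxia, and associated organ toxicity does not alter the grade.
- Item 4c of Protocol 7.8 exempts the rise from AESC status if it falls to Grade 2 or below within 5 days.

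One investigator could put this value in class 4 and another in class 2. The text does not settle it.

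**Step 3. The opening sentence.** Let D mean caused by the disease and M mean consistent with the subject's medications. The sentence records a clinically significant result when it is not D or not M.

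- With a literal *or*, a study-drug effect is not D and is recorded, in line with class 4. But a disease-caused result that no medication explains is not M, so it is also recorded, against class 3.
- If both conditions must hold, disease-caused results drop out, in line with class 3. But a study-drug effect is M if study drug counts as a medication, so it also drops out, against class 4 and Protocol 11.1.1.1.

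Neither reading agrees with all four classes, and the sentence does not say whether study drug counts as a medication.

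**Step 4. Protocol 14.6 against SAP 11.3.** In 14.6 the flag depends only on the normal range, and the grade only on CTCAE. In SAP 11.3 the flag needs two things: out of range, and called significant by the investigator. A class 2 value meets the first and fails the second. The reason given in SAP 5.1, small sample size, explains replacing tables with listings. It does not explain dropping flags that belong in listings.

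**The case against.** The strongest reply is class 4: a clinically significant value is an AE, with no exception for a drug cause. Class 2 states lack of significance as its own condition, so the drug explanation need not be what makes a value non-significant. Protocol 11.1.1.1 and the laboratory endpoint in 14.3.1 also concern only clinically significant findings, so leaving out others contradicts neither. The opening sentence asks for the relationship to study drug, and Table 9 includes laboratory abnormalities among related events, so the scheme clearly expects drug-caused laboratory AEs. All of this stands.

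A reader might therefore infer too much in three ways:

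- **That drug-caused laboratory toxicity is removed from the primary safety endpoint.** The documents support only that it can be left out. The ALT case above is not automatically class 2, and if it is part of CRS, Protocol 11.1.2 has the syndrome recorded and CRS is itself a primary endpoint.
- **That reported incidence shrinks by a known fraction.** Nothing in the documents gives such a fraction. Class 2 holds values judged non-significant, so a fraction of the significant ones is the wrong base. Incidence counts subjects rather than laboratory changes, and no incidence will be reported.
- **That values are hidden.** SAP 11.3 lists every scheduled value.

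It can also be said that the SAP supplements the protocol (SAP section 2), so the flags of 14.6 might be produced anyway. But SAP 11.3 states a specific and narrower rule, and that is the rule a programmer would follow.

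The reply does not remove three things: class 2 has no grade limit, the opening sentence conflicts with the classes on either reading, and the SAP narrows the flags without saying so.

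**Conclusion.** The point holds as an inconsistency in recording and reporting rules. Protocol 11.1.1.3 allows attribution to study drug to weigh against recording a laboratory AE, and SAP 11.3 does not carry the grades and high/low flags that would show such values whatever the investigator decided. Any error from this route leaves out drug-related findings, but how often it would occur cannot be estimated from the documents, and nothing shows that any value was placed in class 2.

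The conclusion rests on two readings: that SAP 11.3 requires both conditions for a flag, and that its silence on laboratory grades means none will be shown. With 4 subjects and listings only, the practical effect is small. The listings are then the main laboratory evidence a reader will have, which is why the SAP change still matters.

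**What to change.** **SAP 11.3.** Flag every out-of-range value as high or low, as Protocol 14.6 states. Add the CTCAE v5.0 grade where one exists. Show the investigator's class from Protocol 11.1.1.3 in its own column. If the narrower rule is intended, name it and justify it in SAP 5.1.

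**Protocol 11.1.1.3.** Limit the medications in the opening sentence to concomitant, non-study medications, and delete the reference to study drug from class 2. Reconcile the sentence with classes 3 and 4 and with 11.1.1.1, and say which governs if they differ. Let class 1 take any value that fails the intervention test, so that the deletion leaves no value without a class. Significance is then decided by the section's own test, and relatedness is recorded separately under 11.1.2.2.

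**Cost.** The SAP change is standard listing programming. The protocol change is a short rewording; because the study has been terminated, it serves mainly as a correction for the record and for any later protocol that reuses the text. The downside is somewhat more laboratory AEs and more flags to read.
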